9.8.8.1.2. Serious Adverse Event

An adverse event should be classified as an SAE if it meets one of the following criteria:

Fatal: Adverse event resulted in death.

Life-threatening: The adverse event placed the subject at immediate risk of death. This

classification does not apply to an adverse event that hypothetically

might cause death if it were more severe.

Hospitalization: The adverse event required or prolonged an existing inpatient

hospitalization. Hospitalizations for elective medical or surgical

procedures or treatments planned before the signing of informed consent

in the study or routine check-ups are not SAEs by this definition.

Disabling/ The adverse event resulted in a persistent or significant incapacity or incapacitating:

substantial disruption of the subject's ability to conduct normal life

functions.

Congenital anomaly

or birth defect:

An adverse outcome in a child or fetus of a subject exposed to the molecule or study treatment regimen before conception or during

pregnancy.

Medically The adverse event did not meet any of the above criteria but could have significant:

jeopardized the subject and might have required medical or surgical intervention to prevent one of the outcomes listed above or involves suspected transmission via a medicinal product of an infectious agent.

9.8.8.1.3. Adverse Drug Reaction

An adverse drug reaction (ADR) in the pre-approval clinical experience with a new medicinal product or its new usages, particularly as the therapeutic dose(s) may not be established, is any noxious and unintended response to a medicinal product related to any dose. The phrase "responses to a medicinal product" means that a causal relationship between a medicinal product and an adverse event is at least a reasonable possibility (ie, the relationship cannot be ruled out).

9.8.8.1.4. Adverse Events of Special Interest

Based on the mechanism of action of etrasimod and prior experience with other agents acting via a similar mechanism, potential adverse events of special interest may be identified. In addition to appropriate reporting of these events as an adverse event or SAE, supplementary detailed information may be collected.

If there are any signs of progressive multifocal leukoencephalopathy (PML)-related symptoms, the Investigator should withhold study treatment and perform appropriate diagnostic evaluation per local standard of care at the first signs suggestive of PML. Typical symptoms associated with PML are diverse, progress over days to weeks, and may include progressive weakness on one side of the body or clumsiness of limbs, disturbance of vision, and changes in thinking, memory, and orientation leading to confusion and personality changes. The Investigator must notify the Medical Monitor of such an event.

Guidance for the Assessment of Potential Progressive Multifocal Leukoencephalopathy is provided in Appendix 5.

9.8.8.1.5. Severity

The severity of each adverse event will be assessed at the onset by a nurse/or physician. When recording the outcome of the adverse event the maximum severity of the adverse event experienced will also be recorded. The severity of each adverse event will be graded according to the Common Terminology Criteria for Adverse Events, version 5.0 (CTCAE v5.0):

Grade 1: Mild; asymptomatic or mild symptoms; clinical or diagnostic

observations only; intervention not indicated.

Grade 2: Moderate; minimal, local or noninvasive intervention indicated;

limiting age-appropriate instrumental activities of daily living (ADL).

Grade 3: Severe or medically significant but not immediately life-threatening;

hospitalization or prolongation of hospitalization indicated; disabling, limiting self-care ADL (eg, preparing meals, shopping for groceries or

clothes, using the telephone, managing money).

Grade 4: Life-threatening consequences, urgent intervention indicated.

Grade 5: Death related to adverse event.

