10.11. Safety Endpoints

- Incidence and severity of adverse events
- Incidence and severity of laboratory abnormalities, and change from baseline in laboratory values (to include hematology, serum chemistry, coagulation, and urinalysis)
- Incidence of clinically significant vital sign abnormalities and changes from baseline

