18.1.1.1. Severity

Severity is classified as Grade 1: Mild, Grade 2: Moderate, Grade 3: Severe, Grade 4: Life Threatening, Grade 5: Death Related to AE, using the Common Terminology Criteria for Adverse Events, version 5.0 (CTCAE v5.0).

All TEAEs will be summarized by SOC, PT, and maximum severity, with SOC and PT presented by descending frequency. If a subject reports a TEAE more than once within a SOC/PT, the AE with the worst-case severity will be used in this summary.

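### The protocol's severity scale lists household tasks as its Grade 3 self-care examples, so Grades 2 and 3 overlap and a Grade 2 event can be recorded as Severe

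*Protocol*

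**What the plan says.** Protocol 9.8.8.1.5 (Severity) states that events are "graded according to the Common Terminology Criteria for Adverse Events, version 5.0 (CTCAE v5.0") and then prints a description of each grade. Grade 2 is moderate and includes events "limiting age-appropriate instrumental activities of daily living (ADL"). It gives no examples. Grade 3 is severe or medically significant and includes events that are "disabling, limiting self-care ADL (eg, preparing meals, shopping for groceries or" and, as the sentence continues, "clothes, using the telephone, managing money". A nurse or a physician assigns the grade at onset, and the maximum severity is recorded with the outcome.

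Protocol 10.11 makes "Incidence and severity of adverse events" a safety endpoint. SAP 18.1.1.1 repeats the labels only ("Severity is classified as Grade 1: Mild, Grade 2: Moderate, Grade 3: Severe", and so on to Grade 5) and names CTCAE v5.0. It then says "All TEAEs will be summarized by SOC, PT, and maximum severity" and, for a subject with repeated events, "the AE with the worst-case severity will be used in this summary". SAP 18.1.6 adds overview rows by maximum severity for all TEAEs and for related TEAEs. SAP 18.1 and Appendix 2 count an event already present before the first APD334-308 dose as treatment-emergent in this study only if its severity rose afterwards.

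**The concern.** The boundary between moderate and severe rests partly on the difference between instrumental and self-care activities. The examples printed under self-care belong to the other class. Cooking, shopping, phoning and handling money are tasks of running a household and living independently; none is care of one's own body. Because Grade 2 has no examples, the only concrete guidance on daily activities pulls instrumental limitations up into Grade 3.

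Three things are at stake. Severe-event counts can be overstated in tables that report a stated safety endpoint. Sites can differ, depending on whether they grade from the protocol page or from CTCAE v5.0 itself. And because a rise in grade decides whether a carried-over event is counted in this study, an unclear boundary between two grades can affect which events are counted as well as the severity column they fall in.

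**Working it through.** The plan gives no figure to reproduce, and the core of the point is textual.

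**Step 1: compare the two entries in Protocol 9.8.8.1.5.**

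| Grade | Functional criterion | Examples printed |
|---|---|---|
| 2 (Moderate) | Limits instrumental activities | None |
| 3 (Severe) | Limits self-care activities | Cooking; shopping for food or clothing; phoning; handling money |

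Take an event whose only functional effect is that the subject cannot shop. By the Grade 2 criterion it is Grade 2. By the Grade 3 examples it is Grade 3. Both readings come from the same page. The examples run on inside the Grade 3 sentence, so text extraction does not explain their position.

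**Step 2: look for a correction elsewhere.** Neither document defines instrumental or self-care activities in any other place. SAP 18.1.1.1 carries labels without functional wording.

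**Step 3: trace where the grade is used.**

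- Maximum-severity tables (SAP 18.1.1.1 and 18.1.6). The worst grade is kept, so an over-grade carries through to the table.
- Treatment-emergent flag for events ongoing from APD334-302 (SAP 18.1, Appendix 2). The error can act in two directions. An unchanged event held at Grade 2 in the parent study and re-read as Grade 3 from the printed examples would be counted as worsened. An event already at Grade 3 because of shopping, which later comes to limit true self-care, would stay at Grade 3 and not be counted.
- Not mandatory treatment discontinuation (Protocol 5.1), seriousness (Protocol 9.8.8.1.2) or efficacy. None of these uses the grade.

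**Step 4: the size of one reclassified subject.** Inputs are about 35 subjects (Protocol 10.2) and 2:1 allocation in the parent study (Protocol 6.1).

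- Etrasimod: 35 × 2/3 = 23.3, about 23. Placebo: 35 × 1/3 = 11.7, about 12.
- One subject moved from Grade 2 to Grade 3 as maximum severity changes the arm's rate by 100/n points: 100/23 = 4.3 points on etrasimod and 100/12 = 8.3 points on placebo.

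The split is an assumption, since SAP 6.5 says that central randomization was not designed to control the allocation ratio in Japan. The step grows as 1/n if an arm is smaller. It reflects the small sample and does not show that any event was misgraded.

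**The case against.** The strongest reply is that the section invokes CTCAE v5.0, and so does the SAP. A rater who uses that scale may not be misled. The Grade 2 entry still covers instrumental limitation expressly, and the Grade 3 entry also speaks of hospitalization and disability, which should deter anyone from grading a missed shopping trip as Severe. This stands in part: it makes misgrading possible rather than certain. It does not remove the overlap, because the protocol prints its own grade descriptions directly after naming the standard and a site can reasonably work from them.

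A second reply is that little depends on the grade. SAP 18 plans no statistical comparison of safety data unless specified, and the comparative list in SAP 18.1.6 does not include severe TEAEs. Grading is blinded and the wording is the same in both arms. This also stands. It confines the effect to descriptive tables and treatment-emergent flagging, and gives no reason to expect bias for or against either arm.

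A third reply concerns the remedy. Protocol 9.8.8.2.2 does not list the basis of the grade among the items recorded, so a query cannot be aimed only at the affected events, and checking Grade 3 alone can only lower grades. The first part stands and widens the query to every Grade 3 event. On the second, the misplaced examples themselves push only from Grade 2 to Grade 3, so checking that direction is appropriate provided it is done blind.

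A reader might also infer that the severe-infection subcategory of special interest (SAP 18.1.5) is inflated. The SAP builds these categories from preferred terms and clinical review and does not tie that subcategory to a CTCAE grade, so the link is not supported.

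**Conclusion.** The concern holds as an internal inconsistency in an operational rule. Protocol 9.8.8.1.5 attaches instrumental tasks to the self-care grade, the two grades overlap, and nothing in either document resolves it. Severe-event counts can be overstated, the worsening test for carried-over events can be blurred, and sites can grade differently. The consequence is limited to descriptive safety summaries and treatment-emergent flagging.

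A reader might conclude that moderate events will be graded Severe and that the severe rates are inflated. The documents do not support that. They do not show which text raters use, how often an event limits only these tasks, or whether any grade was affected. The 4.3 and 8.3 points describe one subject under an assumed 23:12 split and are not an estimate of bias. The reading of the examples as instrumental rests on the plain meaning of the terms; the CTCAE v5.0 text is not reproduced in the documents.

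**What to change.** In Protocol 9.8.8.1.5, move the example list from Grade 3 to Grade 2 and reconcile the Grade 3 self-care wording with the CTCAE v5.0 text that the section already names. Notify sites of the clarification.

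Before unblinding, send a blinded query on all Grade 3 events asking whether the grade rested only on limitation of the listed tasks. Where it did, the investigator reconsiders the grade against the clarified text. For events carried over from APD334-302, recheck the treatment-emergent flag after any change.

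The protocol synopsis plans to integrate these data with APD334-301 and APD334-302, whose protocols are not among the documents. If they share the wording, apply the same clarification there or note the difference in the integrated safety analysis; regrading one study alone would create a new inconsistency.

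The cost is a clarification letter and, in a study of about 35 subjects, a small number of queries.

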9.8.8.1.6. Relationship

The Investigator (or designee) will make a determination of the causal relationship of the adverse event to the study drug using a 4-category system according to the following guidelines:

Not Related: The adverse event is definitely caused by the subject's clinical state or

the study procedure/conditions.

Unlikely Related: The temporal association between the adverse event and the drug is such

that the drug is not likely to have any reasonable association with the

adverse event.

Probably Related: The adverse event follows a reasonable temporal sequence from

administration of the drug and cannot be reasonably explained by the known characteristics of the subject's clinical state, environmental, or toxic factors, or other modes of therapy administered to the subject.

Related: The adverse event follows a reasonable temporal sequence from

administration of the drug, abates upon discontinuation of the drug, follows a known or hypothesized cause-effect relationship, and (if

appropriate) reappears when the drug is reintroduced.

The Investigator will use clinical judgment to determine the relationship. Alternative causes, such as underlying disease(s), concomitant therapy, and other risk factors, as well as the temporal relationship of the event to the study treatment administration should be considered and investigated. The Investigator should consult the IB and the Product Information of marketed products within the drug class, when applicable. For each adverse event/SAE, the Investigator must document in the medical notes that he/she has reviewed the adverse event/SAE and has provided an assessment of causality. There may be situations in which an SAE has occurred and the Investigator has minimal information to include in the initial report to the Sponsor; however, it is very important that the Investigator always make an initial assessment of causality for every event before the initial transmission of the SAE to the Sponsor. The Investigator may change his/her opinion of causality based on subsequent receipt of information and send an SAE follow-up report with the updated causality assessment. The causality assessment is one of the criteria used when determining regulatory reporting requirements.

9.8.8.2. Eliciting and Recording Adverse Events

9.8.8.2.1. Eliciting Adverse Events

Subjects will be instructed that they may report adverse events at any time. An open-ended or nondirected method of questioning should be used at each study visit to elicit the reporting of adverse events.

9.8.8.2.2. Recording Adverse Events

The adverse event reporting period for safety surveillance begins when the subject is initially included in the study (date of first signature of informed consent) and continues up to 30 days after the last study treatment administration. If an adverse event is not resolved or stabilized by this time, the Sponsor in consultation with the Investigator will decide whether to continue to monitor the adverse event or closeout the event in the database if no further follow-up is necessary.

Any SAE suspected to be related to the study treatment must be reported whenever it occurs, irrespective of the time elapsed since the last administration.

Investigators and study personnel will record all adverse events and SAEs whether received through an unsolicited report by a subject, elicited during subject questioning, discovered during physical examination, laboratory testing, and/or other means by recording them on the eCRF and/or SAE Form, as appropriate. The following information should be recorded on the adverse event eCRF:

- Description including onset and resolution dates
- Whether it met SAE criteria
- Severity
- Relationship to study treatment or other causality
- Outcome

For SAEs, events occurring secondary to the primary event should be described on the eCRF in the narrative description field.

The following should be considered when recording SAEs:

- Death is an outcome of an event. The event that resulted in the death should be recorded and reported on the eCRF.
- For hospitalizations, surgical, or diagnostic procedures, the illness leading to the surgical or diagnostic procedure should be recorded as the SAE, not the procedure itself. The procedure should be captured in the narrative as part of the action taken in response to the illness.

9.8.8.2.3. Diagnosis Versus Signs or Symptoms

In general, the use of a unifying diagnosis is preferred to the listing out of individual symptoms. Grouping of symptoms into a diagnosis should only be done if each component sign and/or symptom is a medically confirmed component of a diagnosis as evidenced by standard medical textbooks. If any aspect of a sign or symptom does not fit into a classic pattern of the diagnosis, report the individual symptom as a separate adverse event.

9.8.8.3. Reporting Adverse Events

All SAEs are subject to reporting requirements.

9.8.8.3.1. Serious Adverse Events

Any adverse event considered serious by the Investigator or that meets serious criteria must be reported to the designated safety contact within 24 hours of becoming aware of the event. Enter the SAE information into eCRF, and send other available pertinent information (eg, hospital records, laboratory results) to the designated Sponsor Contact (IQVIA). If additional information is required or becomes available for a previously reported SAE, entry of the new information into eCRF should be completed within 24 hours of awareness.

In case of electronic data capture (EDC) connectivity issues (eg, the eCRF cannot be accessed by the Investigator), the Investigator must complete a Back-Up Paper SAE Report Form and send the form to the designated Sponsor Contact (IQVIA) within **24 hours of investigator awareness of the event.** Once the EDC connectivity is restored, the investigator must enter all pertinent information from the Back-Up Paper SAE Report Form into the eCRF as soon as possible.

For the reporting of Pregnancy/Pregnancy Outcome SAEs, and SAEs occurring after the protocol-defined collection period, the investigator must complete a Back-Up Paper SAE Report Form and send the form to the Sponsor Contact (IQVIA) within 24 hours of investigator awareness of the event.

IQVIA Pharmacovigilance

[contact] (access code [name])

[contact]

Email (preferred method): [contact]

Elective hospitalization and/or surgery for clearly preexisting conditions (eg, a surgery that has been scheduled prior to the subject's entry into the study) will not be reported as an SAE. All other hospitalizations, including elective hospitalizations for any condition that was not preexisting, will be reported as an SAE.

Any SAE that is ongoing when the subject completes the study or discontinues the study will be followed by the Investigator until the event resolved, stabilized, or returned to baseline status.

The Sponsor (via the In-Country Caretaker for Clinical Trial [ICCC]) is responsible for notifying the relevant regulatory authorities of any adverse event assessed by the Reporter (PI) or the Sponsor as:

- a) Serious, unexpected, and related, or
- b) Serious, expected, related and life-threatening or fatal

In addition, the ICCC is responsible for notifying the investigator(s) of active sites, the head(s) of the active study sites, and, if applicable, the institutional review boards (IRBs) of all SAEs occurring during the study that are assessed by the Reporter (PI) or the Sponsor as related and unexpected.

The investigator is responsible for notifying the head of the study site of SAEs and significant safety findings that occur at his or her site. The investigator is also responsible for responding to requests for additional information made by the Sponsor, the head of the study site, or the IRB.

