4. SELECTION OF STUDY POPULATION

The study population consists of men, women and adolescents (hereafter referred to as men and women), 16 to 80 years of age, inclusive, with moderately to severely active UC.

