9.8.8.1.1. Adverse Event

An adverse event is any untoward medical occurrence in a subject or clinical investigational subject administered a medicinal product and which does not necessarily have a causal relationship with this treatment. An adverse event can therefore be any unfavorable and unintended sign, symptom, or disease temporally associated with the use of a medicinal product, whether or not considered related to the medicinal product.

Adverse events can be any of the following:

- Unfavorable changes in general condition
- Subjective or objective signs/symptoms
- Concomitant disease or accidents
- Clinically relevant adverse changes in laboratory parameters over the course of the study
- Preexisting conditions that worsen in severity, increase in frequency, or have new signs/symptoms

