17.1.6. UC-RELATED HOSPITALIZATIONS AND SURGERIES

The UC-related hospitalizations will be captured on the Adverse Event eCRF. The UC-related surgeries, including colectomy, are captured on the Non-Drug Treatment eCRF. Blinded review of AE preferred terms will be performed to determine UC-related hospitalizations.

The UC-related surgeries, including colectomy, will be captured on the Concomitant Non-Drug Treatment eCRF.

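### The protocol gives two different SAE exemptions for hospitalization, so an elective UC admission decided on study is an SAE under one section and exempt under the other

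*Protocol*

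**What the plan says.** **Definition (Protocol 9.8.8.1.2).** An adverse event that requires or prolongs inpatient hospitalization is serious. The exemption covers hospitalizations for elective "procedures or treatments planned before the signing of informed consent" "in the study or routine check-ups are not SAEs by this definition". Apart from check-ups, the test is when the care was planned.

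**Reporting instruction (Protocol 9.8.8.3.1).** The exempt class is "Elective hospitalization and/or surgery for clearly preexisting conditions", illustrated by "eg, a surgery that has been scheduled prior to the subject's entry into the study) will not be reported as an SAE". The next sentence reads: "All other hospitalizations, including elective hospitalizations for any condition that was not preexisting, will be reported as an SAE". Here the test is whether the condition was already present.

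**Related text that bears on the conflict:**
- Protocol 9.8.8.1.1 counts as adverse events "Preexisting conditions that worsen in severity, increase in frequency, or have new signs/symptoms".
- Protocol 9.8.8.2.2 has the site record the illness behind a hospitalization or procedure as the SAE, in place of the procedure.
- Protocol 9.8.8.3.1 opens with a general duty to report, within 24 hours, any adverse event that meets serious criteria.
- Protocol 6.7.3 prohibits major elective surgery during the study.

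**Downstream use (SAP).** Section 18.1.3 identifies SAEs from the seriousness entry on the Adverse Events eCRF. Section 18.1.6 lists serious TEAEs for comparative analysis. Section 17.1.6 states: "The UC-related hospitalizations will be captured on the Adverse Event eCRF". Those admissions are picked out by blinded review of preferred terms. The same section takes UC-related surgery, including colectomy, from the Non-Drug Treatment eCRF.

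**The concern.** The two sections answer the same question with different criteria, and the study disease falls where they disagree. Protocol Section 4 defines the population as people "with moderately to severely active UC", so UC is a preexisting condition in every subject. Neither section excludes the study disease, or a worsened preexisting condition, from its exemption.

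Take a subject whose UC worsens at Week 30 and for whom an elective admission is then arranged. A site working from the definition reports an SAE. A site working from the reporting instruction can conclude that it is told not to report one. SAE classification would then depend on which section a site applies, in a study small enough for single events to move the rates.

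**Working it through.** The check is a comparison of the two rules, followed by one line of arithmetic for scale. The plan gives no figure of its own to reproduce.

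**Step 1. Apply each exemption to the possible cases.**

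| Case | Definition (9.8.8.1.2) | Reporting rule (9.8.8.3.1) | Agree? |
|---|---|---|---|
| Elective surgery for a preexisting condition, planned before consent | Exempt | Exempt | Yes |
| Elective UC admission or surgery decided on study | Not exempt | Exempt as worded | No |
| Elective procedure planned before consent, condition not clearly preexisting | Exempt | Reportable | No |
| Admission for a routine check-up | Exempt | Literally among the other hospitalizations | No, but trivial |
| Non-elective UC admission | Reportable | Reportable | Yes |

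The second row matters. The third should be rare. The fourth has no practical effect, because a routine check-up is not an untoward medical occurrence and so is not an adverse event to begin with.

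**Step 2. Does the example narrow the reporting rule?** It suggests that the authors had pre-planned procedures in mind. But it is introduced as an example, and the sentence after it describes the reportable elective admissions as those for conditions that were not preexisting. It does not describe them as those not planned in advance. The wording therefore keeps the condition test.

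**Step 3. Where would an event be lost?**
- *SAE tables.* These depend on the seriousness entry. SAP 18.1.3 counts a missing entry as serious, but a site applying the exemption would enter non-serious, so that default does not help.
- *UC-related hospitalization summary.* SAP 17.1.6 states no seriousness filter. A flare recorded as a non-serious adverse event still comes under the preferred-term review. The admission drops out of reach only if no adverse event record is made.
- *Colectomy.* It is recorded on the Non-Drug Treatment eCRF and is a rescue procedure under SAP 16.1.2 and Appendix 6. Neither the surgery summary nor the nonresponse rule depends on SAE status.

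**Step 4. Scale of one event.** Inputs are about 35 subjects (Protocol Synopsis and 10.2) and 2:1 allocation in the parent study (Protocol 6.1), assumed to hold in this sample.
- Etrasimod: 35 × 2/3 = 23.3, about 23. One event is 1/23 = 4.3 percentage points.
- Placebo: 35 × 1/3 = 11.7, about 12. One event is 1/12 = 8.3 percentage points.

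**The case against.** The strongest reply is that the protocol, read as a whole, already requires reporting. Worsening UC is an adverse event. If it required admission it meets a seriousness criterion, the opening sentence of 9.8.8.3.1 then demands a report, and 9.8.8.2.2 names the illness as the SAE. An admission needed for a flare is also hard to call elective. On this reading the exempting sentence covers only planned admissions with no new or worsened event, as its example suggests.

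That is probably the intent, and it limits the point to elective admissions and surgery. It does not remove the conflict. The exemption is an express instruction not to report, it sits in the section sites use for reporting, and nothing says that the general provisions override it.

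The prohibition on major elective surgery (Protocol 6.7.3) also has weight. An elective colectomy on study should be uncommon and would be a deviation. But the prohibition does not cover elective medical admissions, and it does not say how a prohibited operation is reported.

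A reader might infer more: that UC admissions and colectomies in general can go unreported, more often on placebo, and that they vanish from the utilization endpoint. The documents do not support that. Non-elective admissions are reportable under both rules, and colectomy has its own record. Placebo subjects may continue background 5-ASA and corticosteroids (Protocol 3.2 and 6.7.2.1), and no text indicates that elective admissions would differ by arm. The hospitalization summary is exposed only where no adverse event is recorded at all.

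**Conclusion.** The two exemptions conflict, and the conflict covers elective UC admissions and surgery decided after consent. For those events the protocol supports opposite SAE classifications. The main exposure is the SAE count and the comparison of serious TEAEs. The UC-related hospitalization summary is a secondary exposure, conditional on a missing adverse event record.

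One reclassified event would shift an arm's SAE rate by about 4 to 8 percentage points. This assumes that about 35 subjects enter and that they split 2:1. SAP 6.5 says the central randomization was not designed to control the allocation ratio in Japan, so the true denominators may differ. The figure is the weight of a single event in a study this size. It does not estimate how often the conflict would arise, which the documents do not allow one to judge, and no bias between arms is shown.

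The point is narrow, but it concerns a stated safety-reporting rule and costs almost nothing to correct.

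**What to change.** 1. Reconcile the exemption in Protocol 9.8.8.3.1 to the test in 9.8.8.1.2, so that the only exempt hospitalizations are those for procedures or treatments planned before consent to this study, and routine check-ups.
2. Add that worsening of a preexisting condition, including UC, that leads to a hospitalization not planned before consent is assessed against the seriousness criteria and reported like any other adverse event. This does not make every UC admission an SAE automatically; it removes the ground for leaving one out.
3. Before database lock, query UC-related adverse events and disease-worsening records for any hospitalization not flagged as serious. Also query UC-related Non-Drug Treatment entries that have no matching adverse event. The second query alone would not find an admission without a procedure.

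The cost is one sentence of clarification, a data query on a small database, and possibly a few more SAE reports.
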